9.2.1 Selection criteria used for the Systematic Literature Review (SLR)

The inclusion and exclusion criteria used for the selection of studies as well as detailed methodology of the systematic literature review are provided in the Appendix 1.

No time period restriction was used. The systematic literature review was conducted to identify all studies (including observational studies and clinical trials) published till 25 June 2018 (search date). In addition, there were no restrictions to the route of administration.

Only 18 studies were shortlisted based on the inclusion criteria. All of the 18 studies were observational studies while no clinical trials were identified that met the inclusion criteria.

The selection criteria utilized in the SLR were the following:

Inclusion criteria

- Population: Pregnant women
- Intervention: Any glucocorticoid or corticosteroid or steroids use irrespective of mode of administration
- Comparator: Any/none
- Outcomes: Incidence/ risk of cleft lip/palate in infants
- Study Design:
 - Meta-analysis and systematic literature reviews
 - Observational studies (such as cohort study, case-control study, registries data)
 - Clinical trials Phase IIb, III, and IV
 - Conference abstracts/posters
- Time period: No time period restriction
- Geography: No geography restriction

Exclusion criteria

- Population: Nonpregnant women
- Intervention: Drugs other than glucocorticoid or corticosteroid or steroid
- Outcomes: Incidence/ risk of cleft lip/palate in infants
- Study Design:
 - Animal Study

- In vitro studies
- o Editorial, letters, comment
- Clinical trials Phase I or preclinical
- Case reports, case series
- o Reviews
- Studies focusing on:
 - Diagnosis and surgical procedure for cleft repair
 - o Impact of Increased internal corticosteroids due to stress
 - The relationship between genetic mutations and cleft patients
 - Adverse events for other drugs
 - Safety profiles of glucocorticoid or corticosteroid

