9.3 Variables

9.3.1 Exposure definition

The primary exposure of interest is glucocorticoid use.

• First trimester exposure: At least one prescription for glucocorticosteroids redeemed from the first day of the last menstrual period to the end of gestational week 12

OR

• Early pregnancy: At least one prescription for glucocorticosteroids redeemed from 30 days before estimated conception to the end of the first trimester

Our primary comparison group includes women not using glucocorticoid during pregnancy.

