9.7 Data analysis

- Direct treatment comparison: Any glucocorticoid or corticosteroid or steroids use irrespective of mode of administration vs. no use of glucocorticosteroids
- Model: Fixed effect model will be used. We assume that the underlying effect size is the same across the studies. The differences in observed effects are only due to random error or sampling error within the studies. The observed effects mainly depend on the sample size and weighted average mean might give a precise estimation of the overall effect. However, any deviation from this assumption will be discussed.
- Measure of relative effect: For the dichotomous outcomes will be assessed by Odds ratio (OR). Given that the event of our interest is a rare outcome, we assume relative risk (RR) equivalent to OR.
- Inverse variance method: Studies with less variance or standard deviation are given more weight. The variance of weighted average can be minimized through this method and hence inverse variance method will be used to assess the direct treatment effect
- Effect size is assessed by Odds ratio (OR) as it is a rare outcome
- Publication bias: Reporting or publication bias will be assessed by using the funnel plot (symmetry or asymmetry) and it again confirmed by using the Egger's test (in case of asymmetry funnel plot). Further, any outliers in the effect size will be determined by Galbraith plot
- Sensitivity analysis: In order to know the robustness of the findings, sensitivity analysis will be performed with and without outlier studies so that any uncertainty can be determined. This will be done only in case of high level of heterogeneity observed. However, plausible reasons for high heterogeneity (unexplained variation) will be discussed in the MAR
- Sub-group analyses will be performed for
 - Route of administration:
 - Topical
 - Systemic
 - Any other form of use
 - Types of orofacial cleft
 - Cleft lip (CP)
 - Cleft lip with or without palate (CLP)
 - Cleft palate (CP)
 - Orofacial cleft (OC)
 - Potency of glucocorticoid
 - Mild
 - Moderate
 - Potent
 - Very potent
- 95% credibility intervals will be used as a measure for the expression of the difference (overlap / no overlap with 1 for OR)
- Data will be analysed by using the metafor package in R software version 3.5.1

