9.9 Limitations of the research methods

- There may have potential biases (recall and publication bias) inherent in retrospective casecontrol design. These types of study may also have higher sensitivity to detect low-frequency defects
- Included studies lacked data evaluating the relationship between dosage and duration of medication and teratogenic effects, which could affect the results of the study.
- Confounding factors assessed and described in the published sources could be an explaining factor for clinical heterogeneity, which includes the decision for a specific treatment / administration of glucocorticosteroids, but also other factors could be a reason for heterogeneityRange of dosages used is relatively wide in included studies which may have an influence on the results
- Conditions of skin, size of the skin surface treated and the part of the body where it is applied were not reported in all studies which may have an influence on the absorption of corticosteroids which may alter effect outcomes

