Sec t	ion 4: Source and study populations	Yes	No	N/A	Section Number
4.1	Is the source population described?	\square			
4.2	Is the planned study population defined in terms of:				
	4.2.1 Study time period	\square			

Sect	tion 4: Source and study populations	Yes	No	N/A	Section Number
	4.2.2 Age and sex		\square		
	4.2.3 Country of origin		\bowtie		9.1, 9.2
	4.2.4 Disease/indication		\bowtie		
	4.2.5 Duration of follow-up		\square		
4.3	Does the protocol define how the study population will be sampled from the source population? (e.g. event or inclusion/exclusion criteria)	\boxtimes			9.1, 9.2

The study is a meta-analysis of published literature. The search criteria for inclusion are described in the protocol.

Sect	ion 5: Exposure definition and measurement	Yes	No	N/A	Section Number
5.1	Does the protocol describe how the study exposure is defined and measured? (e.g. operational details for defining and categorising exposure, measurement of dose and duration of drug exposure)	\boxtimes			9.2.1
5.2	Does the protocol address the validity of the exposure measurement? (e.g. precision, accuracy, use of validation sub-study)		\boxtimes		
5.3	Is exposure categorised according to time windows?	\boxtimes			9.2.1
5.4	Is intensity of exposure addressed? (e.g. dose, duration)		\boxtimes		
5.5	Is exposure categorised based on biological mechanism of action and taking into account the pharmacokinetics and pharmacodynamics of the drug?		\boxtimes		
5.6	Is (are) (an) appropriate comparator(s) identified?	\square			

Comments:

The study does not investigate the validity of exposure assessment, assumes that the selected literature publications fulfill quality standards to address the study objectives. Non-exposure to treatment is deemed the most appropriate comparator.

Sect	ion 6: Outcome definition and measurement	Yes	No	N/A	Section Number
6.1	Does the protocol specify the primary and secondary (if applicable) outcome(s) to be investigated?	\boxtimes			8
6.2	Does the protocol describe how the outcomes are defined and measured?	\boxtimes			9.3.2
6.3	Does the protocol address the validity of outcome measurement? (e.g. precision, accuracy, sensitivity, specificity, positive predictive value, use of validation sub- study)		\boxtimes		

Sect	ion 6: Outcome definition and measurement	Yes	No	N/A	Section Number

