6.4	Does the protocol describe specific outcomes relevant for Health Technology Assessment? (e.g. HRQoL, QALYs, DALYS, health care services utilisation, burden of disease or treatment, compliance, disease management)		\boxtimes		

The study is a meta-analysis of literature. The outcome investigated is orofacial cleft in the offspring of mother exposed to corticosteroids during the first trimester of pregnancy.

Sect	ion 7: Bias	Yes	No	N/A	Section Number
7.1	Does the protocol address ways to measure confounding? (e.g. confounding by indication)		\boxtimes		
7.2	Does the protocol address selection bias? (e.g. healthy user/adherer bias)		\boxtimes		
7.3	Does the protocol address information bias? (e.g. misclassification of exposure and outcomes, time-related bias)		\boxtimes		

Comments:

Reporting or publication bias will be assessed by using the funnel plot (symmetry or asymmetry) and it again confirmed by using the Egger's test (in case of asymmetry funnel plot). Further, any outliers in the effect size will be determined by Galbraith plot

Sect	ion 8: Effect measure modification	Yes	No	N/A	Section Number
8.1	Does the protocol address effect modifiers? (e.g. collection of data on known effect modifiers, sub-group analyses, anticipated direction of effect)	\boxtimes			9.7

Comments:

Sect	ion 9: Data sources	Yes	No	N/A	Section Number
9.1	Does the protocol describe the data source(s) used in the study for the ascertainment of:				
	9.1.1 Exposure? (e.g. pharmacy dispensing, general practice prescribing, claims data, self-report, face-to-face interview)		\boxtimes		
	9.1.2 Outcomes? (e.g. clinical records, laboratory markers or values, claims data, self-report, patient interview including scales and questionnaires, vital statistics)		\boxtimes		
	9.1.3 Covariates and other characteristics?	\square			9.3.3
9.2	Does the protocol describe the information available from the data source(s) on:				
	9.2.1 Exposure? (e.g. date of dispensing, drug quantity, dose, number of days of supply prescription, daily dosage, prescriber)		\boxtimes		
	9.2.2 Outcomes? (e.g. date of occurrence, multiple event, severity measures related to event)		\boxtimes		

Sect	ion 9: Data sources	Yes	No	N/A	Section Number
	9.2.3 Covariates and other characteristics? (e.g. age, sex, clinical and drug use history, co-morbidity, co-medications, lifestyle)		\boxtimes		
9.3	Is a coding system described for:				

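### Non-use is called the most appropriate comparator without a reason, and confounding by indication, which can shift the pooled OR without showing as heterogeneity, has no analysis that separates it

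*Protocol*

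**What the plan says.** - **Comparator.** Protocol section 9.3.1: "Our primary comparison group includes women not using glucocorticoid during pregnancy". Section 9.7 pools "Any glucocorticoid or corticosteroid or steroids use irrespective of mode of administration vs. no use of glucocorticosteroids". Neither requires the non-users to have the condition that led to treatment in the exposed women.
- **Justification.** Annex 2, checklist Section 5 (Comments): "Non-exposure to treatment is deemed the most appropriate comparator". No argument accompanies it.
- **Eligibility.** The literature review admitted studies under "Comparator: Any/none" (section 9.2.1), so comparisons with untreated women who have the same condition were eligible.
- **Decision to treat.** Section 9.9 says that confounding factors described in the sources "could be an explaining factor for clinical heterogeneity, which includes the decision for a specific treatment / administration of glucocorticosteroids". The indication is not named elsewhere in the body of the protocol as a threat to the OR.
- **Checklist answers.** Annex 2 answers No to three items: defining the population by disease or indication (4.2.4), addressing ways to measure confounding, with confounding by indication as the printed example (7.1), and analytic control of confounding (10.5).
- **Subgroups.** Section 7 says the analysis aims to deal with some shortcomings of an existing meta-analysis, naming the confounder effect, through subgroup analyses. It adds that published data will not allow all of them to be addressed. The subgroups in 9.7 are route, cleft type and potency.
- **Interpretation and safeguards.** Section 9.7 describes the inverse-variance result as the direct effect of treatment, uses a fixed-effect model, and reads the 95% interval by whether it overlaps 1. Outliers are sought with a Galbraith plot. The analysis with and without outliers is run only if heterogeneity is high.

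**The concern.** Women prescribed a glucocorticoid generally have a condition that called for it, and often take other treatment for that condition. General non-users mostly do not have it. A comparison of the two groups then carries the condition and its co-medication along with the drug. If either affects cleft risk, the OR moves away from the drug's own effect.

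The protocol's handling is incomplete in three places. The checklist endorses the comparator without qualification, while the same checklist says that confounding by indication is not addressed. Section 9.9 names one consequence of the decision to treat (heterogeneity) and leaves out the other (a shift in the pooled OR). And the subgroups that section 7 relies on do not separate estimates that control for the indication from those that do not: within each route, cleft type or potency, the comparator is still simply non-use.

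The study answers a regulator's question about cleft risk in treated women. Pooling narrows the interval but does not remove a shared bias, so an interval that excludes 1 could reflect the treated condition in part or in whole.

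**Working it through.** The protocol gives no figure for this bias and no sample size or precision calculation (checklist item 10.2 is answered No), so there is nothing to reproduce. What follows illustrates size under assumed inputs.

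**Inputs**
- Cleft rate of 1 in 700 births: protocol section 7.
- 18 studies: sections 9.1 and 9.5.
- Share of exposed women with the indication, p_e: assumed 1.0, varied down to 0.8.
- Share of unexposed women with the indication, p_u: assumed 0.05, varied 0.02 to 0.10.
- Risk ratio of the indication, with co-medication, for cleft, RR_d: assumed 1.0, 1.2, 1.5, 2.0.
- Per-study SE of log OR: assumed 0.3 to 0.5.

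**Step 1. Expected ratio when the drug has no effect**

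Ratio = [1 + p_e(RR_d − 1)] / [1 + p_u(RR_d − 1)]

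With p_e = 1 and p_u = 0.05:

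| RR_d | Calculation | Ratio |
|---|---|---|
| 1.0 | 1.0 / 1.000 | 1.00 |
| 1.2 | 1.2 / 1.010 | 1.19 |
| 1.5 | 1.5 / 1.025 | 1.46 |
| 2.0 | 2.0 / 1.050 | 1.90 |

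At a rate of 1 in 700 the OR is almost the same as this ratio. The exact conversion changes only the last row, from 1.905 to 1.907.

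Over p_e = 0.8 to 1.0 and p_u = 0.02 to 0.10, the OR is 1.14–1.20 for RR_d = 1.2, 1.33–1.49 for RR_d = 1.5 and 1.64–1.96 for RR_d = 2.0. If the comparison is made within the condition, p_e = p_u and the ratio is 1.00 for every RR_d.

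**Step 2. What pooling does to a shared bias**

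Take an OR of 1.43 in every study (p_e = 1, p_u = 0.10, RR_d = 1.5; log OR = 0.358). The pooled SE is SE/√k.
- One study: z = 0.358/0.5 = 0.72 to 0.358/0.3 = 1.19. The chance that the 95% interval excludes 1 is 11% to 22%.
- 18 studies: pooled SE = 0.118 to 0.071, z = 3.0 to 5.1. The chance is 86% to 99.9%.

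With a shared OR of 1.18 the chance rises from 6–9% for one study to 29–65% for 18.

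**Step 3. Would heterogeneity reveal it?**

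If the bias is the same in every study, the between-study variance from this source is zero. Neither a heterogeneity statistic nor an outlier plot would then respond to it.

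If the bias differs, part of it does show. Spread the studies evenly over the four rows of step 1. The log ORs are 0, 0.172, 0.381 and 0.644, with mean 0.299 and variance (0.0896 + 0.0161 + 0.0066 + 0.1191)/4 = 0.058. Then I² = 0.058/(0.058 + SE²):
- SE = 0.5: 0.058/0.308 = 19%
- SE = 0.3: 0.058/0.148 = 39%

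The mean log OR of 0.299 corresponds to an OR of 1.35, with no drug effect. The protocol does not say what level counts as high, so these values may or may not start the sensitivity analysis. Removing outliers would not in any case remove the part of the bias that the studies share.

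**The case against.** - **The 18 studies' comparators and adjustment sets are not visible.** They are in the literature review report (Appendix 1). Section 9.3.1 requires only non-use, so untreated women with the same condition qualify, and some published ORs may already be adjusted for the indication. This stands. A reader might infer that the effect of the disease is in fact pooled as a drug effect; the protocol supports only that it can be.
- **Section 9.9 is not wrong.** It says confounding, including the decision to treat, could explain heterogeneity. With several routes and potencies pooled, indications plausibly differ between studies, and step 3 shows that the bias would then be partly visible. This stands. A reader might infer that the heterogeneity safeguard could never be triggered, but that requires near-identical bias in all 18 studies, which nothing in the document establishes. The section is incomplete, not false.
- **The objectives speak of association, and the checklist says no hypothesis is tested.** True, and direct effect in 9.7 may mean only a pairwise comparison. The wording is still open to a causal reading and is easily changed.
- **The limitation is partly disclosed.** Section 9.9 names the decision to treat, section 7 concedes that published data limit what can be addressed, the Newcastle-Ottawa scale is planned (9.8), and route may partly track indication. These soften the point. But the scale is tied to no analysis, and a route subgroup keeps the same non-user comparator.
- **Extraction detail may belong in the SAP, which is not shown.** This is fair for the coding rules. It does not cover the unqualified checklist sentence, the gap in 9.9, or the list of subgroups that the protocol itself fixes in 9.7.

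**Conclusion.** The point holds as a conditional one. The protocol endorses non-use as the comparator without a reason, describes the decision to treat only as a source of heterogeneity, and plans no analysis that separates estimates controlled for the indication from those that are not. Confounding by indication can therefore shift the pooled OR while the planned checks stay silent.

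Two conditions must both hold: the condition or its co-medication affects cleft risk, and the contributing ORs are neither restricted to nor adjusted for it. The documents settle neither. The size is therefore unknown; the range of 1.00 to 1.90 in step 1 rests wholly on assumed inputs and includes no bias at all.

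This is a cheap improvement, not a flaw that invalidates the analysis.

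**What to change.** 1. **Extraction.** Code each study estimate as (a) compared with untreated women who have the same condition, or restricted to or adjusted for the indication; or (b) compared with general unexposed women without such control.
2. **Section 9.7.** Keep the overall pool. Add a subgroup analysis that reports the pooled OR by this code beside it, and state plainly if stratum (a) is sparse or empty. Describe the pooled OR as an association, not as a direct effect of treatment.
3. **Section 9.9.** Add that confounding by indication can bias the pooled OR without appearing as heterogeneity.
4. **Annex 2, checklist Section 5.** Replace the sentence with a qualified justification: why non-use was chosen, and what it cannot separate.

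The conclusion about the drug should not be made to depend on stratum (a). That stratum may hold few studies, and a real risk could then be relabelled as an effect of the disease through imprecision alone.

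**Cost.** One extraction column, one extra subgroup and a few sentences. Section 9.4 describes extraction as done, while 9.6 has the extraction table still to be created; at most the 18 papers must be reopened for one item. The downside is that the interval in stratum (a) may be wide.

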Annex 3: Additional information

Systematic Literature Review Report (see Appendix 1)

Appendix 1 Systematic Literature Review Report

IMPACT 20638; GC_OC; v 1.2, 16 NOV 2018;

